Appendix 5: New York Heart Association Functional Classification

(The Criteria Committee of the New York Heart Association, 1994)

Class I	Patients have cardiac disease but without the resulting limitations of physical activity. Ordinary physical activity does not cause undue fatigue, palpitation, dyspnea, or anginal pain.
Class II	Patients have cardiac disease resulting in slight limitation of physical activity. They are comfortable at rest. Ordinary physical activity results in fatigue, palpitation, dyspnea, or anginal pain.
Class III	Patients have cardiac disease resulting in marked limitation of physical activity. They are comfortable at rest. Less than ordinary physical activity causes fatigue, palpitation, dyspnea, or anginal pain.
Class IV	Patients have cardiac disease resulting in inability to carry on any physical activity without discomfort. Symptoms of cardiac insufficiency or of the anginal syndrome may be present even at rest. If any physical activity is undertaken, discomfort is increased.

Appendix 6: EDSS Assessment Criteria

EXPANDED DISABILITY STATUS SCALE

- 0 =** normal neurological exam (all FS grade 0)
- 1.0 =** no disability, minimal signs in one FS (one FS grade 1)
- 1.5 =** no disability, minimal signs in more than one FS (more than one FS grade 1)
- 2.0 =** minimal disability in one FS (one FS grade 2, others 0 or 1)
- 2.5 =** minimal disability in two FS (two FS grade 2, others 0 or 1)
- 3.0 =** moderate disability in one FS (one FS grade 3, others 0 or 1) though fully ambulatory; or mild disability in three or four FS (three/four FS grade 2, others 0 or 1) though fully ambulatory
- 3.5 =** fully ambulatory but with moderate disability in one FS (one FS grade 3) and mild disability in one or two FS (one/two FS grade 2) and others 0 or 1; or fully ambulatory with two FS grade 3 (others 0 or 1); or fully ambulatory with five FS grade 2 (others 0 or 1)
- 4.0 =** ambulatory without aid or rest for >500 meters; up and about some 12 hours a day despite relatively severe disability consisting of one FS grade 4 (others 0 or 1) or combinations of lesser grades exceeding limits of previous steps
- 4.5 =** ambulatory without aid or rest for >300 meters; up and about much of the day, characterized by relatively severe disability usually consisting of one FS grade 4 and combination of lesser grades exceeding limits of previous steps
- 5.0 =** ambulatory without aid or rest for >200 meters (usual FS equivalents include at least one FS grade 5, or combinations of lesser grades usually exceeding specifications for step 4.5)
- 5.5 =** ambulatory without aid or rest >100 meters
- 6.0 =** unilateral assistance (cane or crutch) required to walk at least 100 meters with or without resting
- 6.5 =** constant bilateral assistance (canes or crutches) required to walk at least 20 meters without resting
- 7.0 =** unable to walk 5 meters even with aid, essentially restricted to wheelchair; wheels self and transfers alone; up and about in wheelchair some 12 hours a day

- 7.5** = unable to take more than a few steps; restricted to wheelchair; may need some help in transferring and in wheeling self
- 8.0** = essentially restricted to bed or chair or perambulated in wheelchair, but out of bed most of day; retains many self-care functions; generally has effective use of arms
- 8.5** = essentially restricted to bed much of the day; has some effective use of arm(s); retains some self-care functions
- 9.0** = helpless bed patient; can communicate and eat
- 9.5** = totally helpless bed patient; unable to communicate effectively or eat/swallow
- 10.0** = death due to MS

Appendix 7: Guidance on safety monitoring

Patients with recorded elevated blood pressure values (systolic BP >140 and/or diastolic BP > 90 mmHg) should have their blood pressure controlled during the same visit. Patients who have two readings of elevated blood pressure (systolic BP >140 and/or diastolic BP >90 mmHg) should be followed up in one month by an unscheduled visit if the scheduled visit is not due. Should systolic BP >140 and/or diastolic BP >90 mmHg values will be confirmed in the next visit, the patient should be referred to his primary care physician, an independent internist or to the specialty hypertension clinic for evaluation, diagnosis and treatment of hypertension.

Patients with BP values of >160/100 mmHg on any visit during the study should be immediately referred as above for evaluation, diagnosis and treatment of hypertension.

Newly diagnosed hypertension as well as an aggravation of a preexisting condition must be reported as an AE and discontinuation of the study drug must be considered by the investigator.

After a treatment interruption of fingolimod for more than 14 days, patients have to be observed for cardiac events as described in the recommendations for first dose monitoring.

Recommendations for first dose monitoring (also in case of re-initiation of fingolimod after treatment interruption)

Clinicians should be particularly mindful of patients who have a low pulse at baseline (spontaneously or through drug induced β -receptor blockade), prior to administration of the study drug.

Be aware that fingolimod causes transient heart rate lowering and may cause AV conduction delays following initiation of treatment. This also applies to recommencing treatment after an interruption of more than 14 days.

All patients will be monitored for a period of at least 6 hours for signs and symptoms of bradycardia. The monitoring includes a 12-lead ECG prior and 6 hours after the first dose, continuous 6-hour ECG recording (recommended) after the first dose as well as blood pressure and heart rate measurement every hour. Should post-dose bradyarrhythmia-related symptoms occur, appropriate clinical management should be initiated and observation should be continued until the symptoms have resolved.

If the patient's heart rate at the end of the 6-hour period is the lowest following first dose administration, the monitoring should be extended by at least 2 hours and until the heart rate increases.

In those patients with evidence of clinically important cardiac effects during the first 6 hours, monitoring should be extended according to local label.

Should a patient require pharmacologic intervention during the first dose observation, overnight monitoring with continuous ECG in a medical facility should be instituted and the first dose monitoring strategy should be repeated after the second dose of fingolimod.

Because of additive effects on heart rate, Fingolimod is not recommended in patients receiving beta blockers or other substances which may decrease heart rate. Fingolimod should not be co-administered [for Switzerland: is contraindicated] with Class Ia (e.g. quinidine, procainamide) or Class III (e.g. amiodarone, sotalol) antiarrhythmic medicinal products).

Recommendations for management of bradycardia

Be aware that fingolimod causes transient heart rate lowering and may cause AV conduction delays following initiation of treatment. This also applies to recommencing treatment after an interruption of more than 14 days.

All patients should be observed for a period of at least 6 hours for signs and symptoms of bradycardia (according to local label). Should post-dose bradyarrhythmia-related symptoms occur, appropriate clinical management should be initiated and observation should be continued until the symptoms have resolved.

Monitoring measures will be implemented as foreseen by the local label

Clinicians should be particularly mindful of patients who have a low pulse (<55bpm) at baseline (spontaneously or through drug induced β -receptor blockade), prior to administration of the study drug.

Atropine (s.c. or i.v.) is recommended as the first line treatment of bradycardia, up to a maximum daily dose of 3 mg.

Furthermore, the common guidelines for treatment of bradycardia (e.g. ACLS guidelines) should be followed as appropriate:

- In case of clinical symptoms or hypotension, administration of atropine 1 mg, repeated administration in 3-5 minutes
- If heart rate and/or blood pressure remains unresponsive, consider administration of dopamine drip 5-20 $\mu\text{g}/\text{kg}/\text{min}$ or epinephrine drip 2-10 $\mu\text{g}/\text{min}$
- Performance of transcutaneous pacing may also be considered

In the setting of decreased blood pressure, isoproterenol should be avoided/used with caution.

Guidance on monitoring of patients with elevated liver function tests

In case of detection of elevated ALT/AST values > 5 times the upper limit of the normal range (ULN), additional blood chemistry panel including ALT, AST, AP, GGT, total and conjugated bilirubin, albumin should be performed.

If ALT/AST values are repeatedly 5 times the ULN, the study drug must be suspended and not resumed until values have normalized. Patients who develop symptoms suggestive of hepatic dysfunction such as unexplained vomiting or jaundice, should have liver enzymes checked and fingolimod should be discontinued if significant liver injury is confirmed.

In case of isolated elevation of bilirubin over 2.0 mg/dl (34.2 $\mu\text{mol}/\text{L}$), the investigator must discontinue fingolimod administration. Additional evaluations may be performed at the discretion of the investigator.

An interruption or discontinuation of the study drug should be clearly documented and reflected on Dosage Administration Record CRF. AE/SAEs need to be filed as appropriate.

Guidance on monitoring of patients with notable lymphopenia

Fingolimod results in sequestration of a proportion of the circulating lymphocytes in lymph nodes with resultant reduction in circulating lymphocyte counts. Average circulating lymphocytes counts are expected to be around $0.5 - 0.6 \times 10^9 / \text{L}$ or 500- 600 cells/ mm^3 . As such, the absolute total WBC, neutrophil and lymphocyte counts will be measured at each visit by the local laboratory. In case of lymphocyte alert, lymphocyte count should be

repeated in two weeks by the local laboratory. If the repeat test confirms the lymphocyte count is below $0.1 \times 10^9/L$ or 100 cells/mm^3 , the study drug must be discontinued and the lymphocytes count needs to be monitored every two weeks until levels reach $0.6 \times 10^9/L$ values. Recovery of lymphocyte counts is expected to take several weeks given the long half-life of fingolimod. The patient should be evaluated and monitored for infections on a regular basis during this period. As shown recently (data presented at AAN 2011: S30.001 Lymphocytes and Fingolimod-Temporal patterns and relationship with infections) a lymphocyte count between $100\text{-}200 \text{ cells/mm}^3$ is not associated with a higher infection risk. Therefore, a cut-off of 100 cells/mm^3 is regarded as appropriate for this study. After termination of the study the recommendations defined in the local label will prevail, in Germany a limit of 200 cells/mm^3 will be considered in agreement with the SmPC.

Re-initiation of the study drug can only be considered once the lymphocyte counts increase above 600 cells/mm^3 as confirmed by the local lab after discussion with the Clinical Trial Leader at Novartis.

Guidance on monitoring of patients with symptoms of neurological deterioration, inconsistent with MS course

Should a patient develop any manifestations that, in opinion of the investigator, are atypical for multiple sclerosis including unexpected neurological or psychiatric symptom/signs (e.g. rapid cognitive decline, behavioral changes, cortical visual disturbances or any other neurological cortical symptoms/sign), or any symptom/sign suggestive of an increase of intracranial pressure or accelerated neurological deterioration, the investigator should schedule a complete physical and neurological examination and an MRI as soon as possible and before beginning any steroid treatment. Conventional MRI as defined in the protocol as well as Fluid-attenuated Inversion Recovery (FLAIR) and Diffusion-weighted imaging (DWI) sequences are recommended for differential diagnosis of Posterior reversible encephalopathy syndrome. The MRI must be evaluated by the local neuroradiologist. The investigator will contact the Clinical Trial Leader at Novartis to discuss findings and diagnostic possibilities as soon as possible. AE/SAEs need to be filed as appropriate.

In case of new findings in the MRI images in comparison with the previous available MRI which are not compatible with MS lesions, the study drug will be discontinued and other diagnostic evaluations need to be performed at the discretion of the investigator. In case of presence of new hyperintense T2-weighted lesions in the MRI which may be infectious in origin it is recommended to collect a cerebrospinal fluid sample if indicated. Analysis of the CSF sample including cellular, biochemical and, microbiological analysis (e.g. herpes virus, JC virus), to confirm/exclude an infection (e.g. PML) should be performed. In the event of suspected CNS infection, a CSF aliquot should in consultation with the sponsor be sent to a central laboratory (to be designated by the sponsor) for confirmatory testing.

Only when the differential diagnosis evaluations have excluded other possible diagnosis than MS and after discussion with the Clinical Trial Leader at Novartis, the study drug may be restarted.

Guidance on monitoring of patients with infections

All infections that develop during the study will be reported as AEs. Investigators are requested to specifically ask about infections at each visit. In case of infections an

unscheduled visit should be conducted. Treatment and additional evaluations will be performed at discretion of the investigator.

The investigator should remind the patient of the risk of infections and to instruct them to promptly report any symptoms of infections to the investigator. The patients must also be reminded to always carry their Patient Information Card (with site contact information and which identifies them as participants in a clinical study with an investigational agent with potential immunosuppressive effects) and to show this to any local healthcare provider they may consult and ask that the investigator be contacted.

When evaluating a patient with a suspected infection, the most sensitive tests available should be used (i.e. that directly detect the pathogen, as with PCR).

The investigator should consider early treatment with specific antimicrobial therapy on the basis of clinical diagnosis or suspicion thereof (e.g. antiviral treatment for herpes simplex or zoster) in consultation with infectious disease experts, as appropriate. The investigator should inform the Novartis medical expert of any such cases.

Investigators should consider the added immunosuppressive effects of corticosteroid therapy for treatment of MS attack/relapse and increase vigilance regarding infections during such therapy and in the weeks following administration.

Guidance for Ophthalmic Monitoring

Fingolimod has previously been associated with a two-fold increase in the risk of macular edema in renal transplant patients receiving cyclosporine. Although there have been no confirmed cases of macular edema in the multiple sclerosis Phase II study, careful ophthalmic monitoring is being implemented to permit early detection of this event, should it occur. A complete ophthalmic examination by an ophthalmologist will be conducted in accordance with [Table 7-1](#). Similar assessments must be performed at an unscheduled ophthalmology visit for any patient who presents with new visual symptoms or decrease in visual acuity. The following assessments will be performed at the ophthalmic examinations:

1. Best corrected visual acuity using a visual acuity chart with equal spacing between letters and between lines
2. Dilated ophthalmoscopy for inspection of the macula and the optic disc
3. Optical Coherence Tomography (OCT)

Guidance on monitoring patients for possible macular edema

At baseline, if there is a suspicion of macular edema by dilated ophthalmoscopy or OCT (increased central foveal thickness or cystic changes in the fovea), the patient not be enrolled. A fluorescein angiogram may be performed to rule out vascular leakage in such cases. Based on ophthalmic monitoring during the study, study drug must be discontinued in any patient who meets one of the following criteria:

- Patient who is diagnosed to have macular edema
- Patient who has a decrease in visual acuity (2 line or greater loss on low or normal contrast chart) and an abnormal OCT (> 20% increase in central foveal thickness compared to baseline OCT or cystic changes in the fovea)

A fluorescein angiogram is recommended to evaluate for the presence of vascular leakage in these patients and patients must be encouraged to stay in the study to track resolution of these changes during subsequent visits.

These patients must be followed-up 1 month and 3 months after diagnosis of macular edema and more frequently if needed based on the ophthalmologist's judgment. Further ophthalmologic evaluations until such time as resolution is confirmed or no further improvement is expected by the ophthalmologist (based on a follow-up period of not less than

3 months). These evaluations will include repeat best-corrected visual acuity, fundus examination, and OCT. Fluorescein angiography (FA) is repeated at the discretion of the ophthalmologist. If the patient does not show definite signs of improvement on examination by specialist testing (e.g. OCT, FA) after 6-8 weeks after discontinuation of study drug, then therapy for macular edema in conjunction with an ophthalmologist experienced in the management of this condition should be initiated.

An interruption or discontinuation of the study drug should be clearly documented and reflected on Dosage Administration Record eCRF. AE/SAEs need to be filed as appropriate. For patients discontinuing study drug for any of the above ophthalmic reasons, copies of the colored OCT and fluorescein angiography (if performed) as well as source documents of ophthalmic examination should be kept at the site as source documents. These documents may need to be submitted for review by an independent panel if needed.

2.8.1 Adverse events (AEs).....	13
2.8.2 Deaths.....	13
2.8.3 Laboratory data	13
2.8.4 Other safety data	13
2.9 Pharmacokinetic endpoints.....	14
2.10 PD and PK/PD analyses.....	14
2.11 [REDACTED].....	14
2.12 Biomarkers.....	14
2.13 Not applicable.Other Exploratory analyses	14

List of abbreviations

AE	Adverse event
ATC	Anatomical Therapeutic Classification
CRF	Case report/record form
CSP	Clinical Study Protocol
CSR	Clinical Study report
██████	██
FAS	Full Analysis Set
MedDRA	Medical Dictionary for Drug Regulatory Affairs
██████	██
OCT	optic coherence tomography
██████	██
██████	██
PPS	Per-Protocol Set
██████	██
██████	██
RAP	Report and Analysis Process
RNFL(T)	retinal nerve fiber layer (thickness)
RRMS	relapsing remitting multiple sclerosis
SAF	Safety Set
SAP	Statistical Analysis Plan
██████	██
SOC	System Organ Class
TFLs	Tables, Figures, Listings
TMV	Total Macular volume

1 Introduction

This statistical analysis plan (SAP) describes the statistical methods for the final analysis of this study. The final statistical analysis serves as basis for the Clinical Study Report (CSR). This SAP displays the analysis of the PASSOS study and has the following reference documents:

- Study Protocol, Version 4.0 (Original protocol incl. Amendment 4), dated 26-JUL-2016

1.1 Study design

This is a multi-center, open-label study in RRMS patients treated with fingolimod. After signing the informed consent, patients will enter a Screening Phase (day -28 to day 0) before starting the study at Baseline (visit 2/day 0), followed by a 36-month longitudinal data collection phase. Visits are performed at month 3 (visit 3), month 6 (visit 4), month 12 (visit 5), month 24 (visit 6), and month 36 (visit 7). Eligibility will be determined at Screening. OCT and other assessments will be performed according to the schedule in Table 7-1 of the Clinical Study Protocol (CSP).

1.2 Study objectives and endpoints

The primary objective is to evaluate the change in average RNFL thickness (RNFLT) in RRMS patients treated with fingolimod over 36 months as assessed by OCT. The average RNFL thickness following OCT assessment will be calculated for the left and right eye per visit and per patient. The following table describe the objectives and endpoints:

	Objective	Endpoint
Primary	To evaluate the change in average RNFL thickness (RNFLT) in RRMS patients treated with fingolimod over 36 months as assessed by OCT	Absolute Difference in mean RNFLT from baseline (BL) to M36 (or last values in case of missing data) in the full analysis set (FAS). Mean RNFLT is the average of valid measurements of right and left eye. Sensitivity analyses are performed with the Per-Protocol Set (PPS) and for relative change (M36/BL)
Secondary	To compare changes in OCT parameters between eyes with and without history of optic neuritis	Absolute Difference in RNFLT from baseline (BL) to M36 (or last values in case of missing data) in the full analysis set (FAS) for: - eyes with versus without optic neuritis
Secondary	To evaluate the change in average RNFLT under fingolimod therapy from	Absolute Difference and ratios in average RNFLT from baseline (BL) to M12 respectively M24 (or last values in case of missing data) in the full analysis set (FAS).

	Objective	Endpoint
	baseline to months 12 and 24 as assessed by OCT	
Secondary	To evaluate change in quadrant RNFLT under fingolimod therapy from baseline to months 12, 24 and 36	
Absolute Difference and ratios in average quadrant RNFLT from baseline (BL) to M12, resp. M24 resp. M36 (or last values in case of missing data) in the full analysis set (FAS).
 
Quadrant RNFLT are:
 
 - Nasal-inferior - Nasal-superior - Temporal.inferior - Temporal-superior
Secondary	To evaluate changes in total macular volume (TMV) under fingolimod therapy from baseline to months 12, 24 and 36	Absolute Difference and ratios in average TMV from baseline (BL) to M12, resp. M24 resp. M36 (or last values in case of missing data) in the full analysis set (FAS).
Secondary	To evaluate changes in ganglion cell layer thickness (GCLT) under fingolimod therapy from baseline to months 12, 24 and 36	Absolute Difference and ratios in average GCLT from baseline (BL) to M12, resp. M24 resp. M36 (or last values in case of missing data) in the full analysis set (FAS).
Secondary	To evaluate safety and tolerability of fingolimod in MS patients followed for up to 36 months and specifically to determine the frequency of macular edema under treatment with oral fingolimod in this patient population	
Incidence of adverse events, serious adverse events and (S)AEs at least possible related to fingolimod in the Safety Set (SAF)
 
Incidence of macular edema (AE of special interest)

Last value until Visit x The last (post-baseline) value documented until Visit x, i.e. missing or invalid data are replaced by the last available value. Baseline values are not carried forward.

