3.2 Secondary objectives

To evaluate the change in average RNFLT under fingolimod therapy from baseline to months 12 and 24 as assessed by OCT

[figure not shown]
To evaluate change in quadrant RNFLT under fingolimod therapy from baseline to months 12, 24 and 36

To evaluate changes in total macular volume (TMV) under fingolimod therapy from baseline to months 12, 24 and 36

To evaluate changes in ganglion cell layer thickness (GCLT) under fingolimod therapy from baseline to months 12, 24 and 36

To compare changes in OCT parameters between eyes with and without history of optic neuritis and between right and left eye

[figure not shown]
To evaluate safety and tolerability of fingolimod in MS patients followed for up to 36 months and specifically to determine the frequency of macular edema under treatment with oral fingolimod in this patient population

4 Study design

This is a multi-center, open-label study in RRMS patients treated with fingolimod. After signing the informed consent, patients will enter a Screening Phase (day -28 to day 0) before starting the study at Baseline (day 0), followed by a 36-month longitudinal data collection phase (see Figure 4-1). Eligibility will be determined at Screening. OCT and other assessments will be performed according to the schedule in Table 7-1.

Figure 4-1 Study outline

5 Population

In this study approximately 100 patients with MS are expected to be enrolled in Germany and Switzerland.

The investigator must ensure that all patients who meet the following inclusion and do not fulfill any of the exclusion criteria are offered enrollment in the study. No additional exclusion parameters can be applied by the investigator, in order that the study population will be representative of all eligible patients.

Patients who drop out after baseline during the longitudinal phase will not be replaced.

The study is planned to be conducted at approximately 10 sites in Germany and approximately 1 site in Switzerland.

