2.8.1 Adverse events (AEs)

Adverse events which started before BL/M0 were listed only. Analyses were performed on AEs which started at/after BL/M0.

The incidence of adverse events is displayed with n, percentage and 95% confidence interval for the SAF. Here, different types of AEs are presented:

- (1) Any AE
- (2) AE with suspected relationship to fingolimod
- (3) AE leading to study drug dosage adjustment/temporary interruption
- (4) AE leading to permanent study drug discontinuation
- (5) Serious adverse event
- (6) Non-Serious AE
- (7) Death

For AEs of type (1) to (6) a two-level frequency table for MedDRA system organ classes (SOC) and Preferred Terms (PT) within SOC are presented. Here, a patient with multiple occurrences is counted only once on the respective class.

The maximum severity of (several) AEs occurring in a patient ist displayed for PTs within SOC, SOC and overall.

For AEs of type (7), (5), and (3) separate listings are generated.

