2.8.1.1 Adverse events of special interest / grouping of AEs

Not applicable

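### Macular-edema incidence is a named secondary endpoint, but the SAP's section on AEs of special interest plans nothing for it: no grouped count, no interval of its own, no guaranteed row at zero cases

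*SAP*

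**What the plan says.** Protocol 3.2 includes a general safety and tolerability objective and then singles out one event: "specifically to determine the frequency of macular edema under treatment with oral fingolimod". SAP 1.2 turns this into its own line in the endpoint table: "Incidence of macular edema (AE of special interest").

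SAP 2.8.1.1 carries the heading "Adverse events of special interest / grouping of AEs". Its entire content is that the section does not apply.

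SAP 2.8.1 states: "The incidence of adverse events is displayed with n, percentage and 95% confidence interval for the SAF". It then names seven types: any AE, AEs suspected to be related to fingolimod, AEs leading to dose adjustment or temporary interruption, AEs leading to permanent discontinuation, serious AEs, non-serious AEs, and deaths. Types (1) to (6) also get a frequency table by system organ class and preferred term, with each patient counted once per class. On listings it says: "For AEs of type (7), (5), and (3) separate listings are generated". AEs that began before baseline are listed and not analysed.

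**The concern.** The SAP promises an endpoint in one section and disclaims it in the section where its analysis should be specified. A programmer working from section 2.8 would find no instruction to produce a macular-edema result. Three things are then left to chance: which coded terms are added together, whether an interval is given, and whether the event appears at all when the count is zero.

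The zero-case situation is the important one. This is the only safety event named in the objectives, the study is small, and no case or very few cases is a realistic outcome. An objective to determine a frequency is not met by a table in which the event is simply absent, because the reader then has no statement of how large an incidence the data leave open.

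**Working it through.** **Figures in the plan.** There is none to reproduce. The sample size of about 100 (protocol 10.7, SAP 3) is described as a representative sample for an explorative study and rests on no rate, precision or power. The core of the check is a comparison of sections; the arithmetic shows only what the missing interval would say.

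**Step 1: what section 2.8 would deliver as written.** Case counts are assumed, N = 100.

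- No case: a frequency table of reported terms has no macular-edema row unless the table shell forces one.
- One case: one preferred-term row, 1 (1%), with no interval attached to it.
- Two patients coded to the same term: one row, 2 (2%), with no interval.
- Two patients coded to two different terms: two rows of 1 (1%) each, with no total. Rows cannot safely be added by the reader, because a patient with both terms would be counted in both.

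Whether cases would be spread over several terms cannot be told from the documents. That is why the list should be fixed in advance.

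**Step 2: the interval.** For x cases in n patients, the exact (Clopper-Pearson) 95% limits are the 2.5% quantile of Beta(x, n − x + 1) and the 97.5% quantile of Beta(x + 1, n − x). For x = 0 the lower limit is 0 and the upper limit is 1 − 0.025^(1/n):

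- n = 100: 1 − 0.025^(1/100) = 3.62%
- n = 80 (an assumed smaller safety set): 1 − 0.025^(1/80) = 4.51%

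| Cases | N = 100 | N = 80 |
|---|---|---|
| 0 | 0% (0 to 3.62%) | 0% (0 to 4.51%) |
| 1 | 1% (0.03 to 5.45%) | 1.25% (0.03 to 6.77%) |
| 2 | 2% (0.24 to 7.04%) | 2.5% (0.30 to 8.74%) |
| 3 | 3% (0.62 to 8.52%) | 3.75% (0.78 to 10.57%) |

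The method should be named, since SAP 2.8.1 does not name one for its intervals. A normal approximation gives 0 to 0 when x = 0. For 1 of 100 it gives 1% ± 1.96 × √(0.01 × 0.99 / 100) = 1% ± 1.95%, that is −0.95% to 2.95%, with a negative lower limit and an upper limit well below the exact 5.45%.

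**Step 3: how likely is a zero count?** P(no case) = (1 − p)^n. The documents give no expected incidence, so p is an assumed range.

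| True incidence p | N = 100 | N = 80 |
|---|---|---|
| 0.5% | 0.995^100 = 61% | 67% |
| 1% | 0.99^100 = 37% | 45% |
| 2% | 0.98^100 = 13% | 20% |

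**Step 4: what the figure would estimate.** Inclusion criterion 5 requires 28 days to 4 months of fingolimod before screening, and screening can last up to 28 days. Time on drug at baseline therefore runs from 28 days to about 122 + 28 = 150 days. SAP 2.8.1 analyses only AEs starting at or after baseline, and protocol Appendix 7 bars enrolment "if there is a suspicion of macular edema by dilated ophthalmoscopy or OCT" at baseline. The result is incidence from baseline onward among patients already treated, not incidence from first dose.

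**The case against.** The best defence is that the endpoint is not lost. SAP 1.2 itself commits to an incidence. A case coded as macular edema would be counted in the preferred-term tables, including the table for permanent discontinuations where that applies. SAP 2.8.1 does contain a commitment to 95% intervals for AE incidence. Whether a zero row is printed depends on table shells that are not part of the public text, and parts of the SAP are not visible. All of this stands. It limits the point to an unresolved inconsistency and an unassigned interval. It does not remove the point, because the disclaimer in 2.8.1.1 is legible and cannot be squared with 1.2.

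On case definition, Appendix 7 separates "Patient who is diagnosed to have macular edema" from "Patient who has a decrease in visual acuity (2 line or greater loss on low or normal contrast chart) and an abnormal OCT". A reader might infer that the endpoint is undefined. These are criteria for stopping study drug, not endpoint definitions, and the natural reading of an AE endpoint is that a reported diagnosis counts. Saying so would be a clarification.

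On the time window, SAP 2.8.1 already restricts analysis to events from baseline, and SAP 2.4.1 acknowledges the pre-treatment. Only a label is missing.

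On listings, the gap is narrow: a non-serious case leading to permanent discontinuation is counted under type (4) but not listed. Serious cases, and those leading to dose adjustment or temporary interruption, are listed.

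**Conclusion.** The point holds as an inconsistency between SAP 1.2 and SAP 2.8.1.1, with a practical consequence: the one safety event named in the objectives has no grouped count, no interval of its own and no guaranteed row at zero. No figure in the documents is wrong. The size is that of the unreported uncertainty: with about 100 patients, zero cases leaves up to 3.6% open (4.5% with 80), and zero cases has a probability of 13% to 61% for assumed incidences of 2% down to 0.5%. It should be corrected, and the correction is cheap.

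Three stronger readings are not supported:

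- That macular edema would be reported nowhere: any coded case enters the preferred-term tables.
- That the SAP plans no confidence interval for AEs: it does, for seven types, but not for this one.
- That notable laboratory values under protocol Appendix 3 can reach no table: protocol 8.1 and SAP 2.8.3 make an abnormal value an AE when it causes signs or symptoms, is clinically significant, or requires therapy or discontinuation, and such AEs are tabulated. What has no planned tabulation is a notable value not recorded as an AE. No laboratory endpoint is promised, SAP 2.8.3 states its choice openly, and it is unclear whether the values are in the database, so this is a side note only.

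**What to change.** In SAP 2.8.1.1, replace the disclaimer with macular edema as a grouped AE of special interest:

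- Fix the list of preferred terms before database lock, for example at the planned data review meeting. State there whether a reported diagnosis is required, or whether patients meeting only the acuity-plus-OCT criterion of Appendix 7 also count.
- Report patient-level n/N, percentage and exact (Clopper-Pearson) 95% interval in the safety set, printed even if n = 0.
- Add a short listing of all cases, whatever their seriousness or the action taken with study drug.
- Label the result as incidence at or after baseline in patients already on fingolimod.

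The cost is a term list, one table row and one brief listing. No data collection or clinical rule changes.

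Optional: protocol 7.6.3 tells sites to keep abnormal laboratory values off the AE form and record the associated diagnosis, sign or symptom, while 8.1 makes some abnormal values AEs. The two can be read together, but SAP 2.8.3 depends on that route, so the wording should be reconciled.
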